2.2 Safety

All operative site events occurring at any time as well as all serious adverse events (SAEs) occurring in the perioperative period (intraoperative to hospital discharge) will be collected and compared to published data. It is expected that the AE rates reported for the Secur-Fit Advanced Hip Stem will be comparable to those reported in the literature for other primary femoral stems on the market. Details regarding AE definitions, recording and reporting are in Section 8 of this protocol, Adverse Events.

3 Clinical Study Plan

3.1 Study Design

A prospective, post-market, multi-center design will be employed. Radiographs will be assessed by an independent reviewer.

3.2 Number of Centers

3.2.1 Centers for Standard Data Collection

Cases will be enrolled at five to eight centers. The enrollment goal is approximately 41 cases per center utilizing the Secur-Fit Advanced Hip Stem but will vary dependent upon the number of participating centers. Although a goal is presented, there is no maximum limit to the number of cases that a center may enroll. In the event that a center far exceeds the enrollment goal, Stryker may ask the center to cease enrollment so as not to skew the data. All participating centers will comply with the federal regulations regarding patient informed consent and Institutional Review Board (IRB) or Ethics Committee (EC)

approval. Non-compliance of a study center may result in termination of the center's participation in the study.

3.3 Number of Subjects

Cases will be enrolled until a total of 314 cases receive the Secur-Fit Advanced Hip Stem.

3.4 Estimated Study Duration

The enrollment period is estimated to be a maximum of 24 months; cases will be evaluated as per the evaluation schedule until each case reaches 10 years.

To allow for a learning curve with the use of the device, enrollment of cases into the study will commence when three cases have been completed at the center using the Secur-Fit Advanced Hip Stem.

4 Eligibility

The following criteria will be used to distinguish patients eligible for enrollment into this study. Proper implant selection must consider design, fixation, and environmental variables including: patient weight, age, bone quality and size, activity level and pre-operative level of health, as well as the surgeon's experience and familiarity with the device.

4.1 Inclusion Criteria

- A. Patient has signed an IRB/EC approved, study specific Informed Patient Consent Form.
- B. Patient is a male or non-pregnant female, skeletally mature and age 21-75 years at time of study device implantation.
- C. Patient has a diagnosis of Non-Inflammatory Degenerative Joint Disease.
- D. Patient is a candidate for primary cementless total hip arthroplasty.
- E. Patient is willing and able to comply with postoperative scheduled clinical and radiographic evaluations and rehabilitation.

4.2 Exclusion Criteria

- F. Patient has previously undergone open surgical intervention on the operative hip.
- G. Patient has a prior femoral fracture, with or without deformity, on the operative side.
- H. Patient has an existing total hip replacement on the contralateral side.
- I. Patient requires simultaneous bilateral total hip replacement.
- J. Patient has a Body Mass Index (BMI) > 45.
- K. Patient has an active or suspected latent infection in or about the affected hip joint at time of study device implantation.
- L. Patient has a neuromuscular or neurosensory deficiency that would create an unacceptable risk of instability, prosthesis fixation failure or complications in postoperative care, or which limits the ability to evaluate the safety and efficacy of the device
- M. Patient has bone stock that is inadequate for support or fixation of the prosthesis, or is diagnosed with a systemic disease (e.g. Lupus Erythematosus) or a metabolic disorder (e.g. Paget's disease) leading to progressive bone deterioration.
- N. Patient is immunologically suppressed or receiving steroids in excess of normal physiological requirements (e.g. > 30 days).
- O. Patient has a known sensitivity to device materials.
- P. Patient is a prisoner.

5 Subject Enrollment

5.1 Treatment Assignment

All subjects will receive the Secur-Fit Advanced Hip Stem.

5.2 Randomization

The study will enroll under a non-randomized study design.

6 Device Description

6.1 Study Device

The Secur-Fit Advanced Hip Stem has been cleared for use in the United States; therefore, this study is considered a post-market assessment. All cases in this study will receive the Secur-Fit Advanced Hip Stem.

The Secur-Fit Advanced Hip Stem is a straight stem intended for cementless, press-fit application. It is a non-porous coated femoral stem with a fit and fill design to provide rotational stability. The stem body design is based on the Secur-Fit HA Hip Stem. Like the predicate for body design, the Secur-Fit Advanced Hip Stem is a straight stem with a normalization pattern on the anterior and posterior aspects of the proximal end (depicted in Figure 1) to facilitate press-fit stability and load transmission to the proximal region of the femur. Based on 3-Dimensional simulations, these normalizations are designed to convert medial and lateral shear stresses to compressive forces, which may facilitate proximal loading.(RD-13-001). Medial curvature of the stem is proportional and size-specific.

The Secur-Fit Advanced Hip Stem will be fabricated from Titanium (Ti-6Al-4V) Alloy, with a CPTi plasma spray coating covered with a HA powder (Pure-Fix HA). The distal portion of the stem has a polished tip, and the neck region has been polished and shot peened.

The Secur-Fit Advanced Hip Stem will be available in 9 sizes ranging from size 4 through 12; the catalog numbers are listed in Table 1. Stem length will range from 110 mm to 160 mm, increasing in length as the stem size increases. Stem length is measured from the medial calcar point to the distal tip of the stem. The stem's neck is designed with a Howmedica Osteonics V40 taper on the proximal end similar in design to the Accolade II.

V40 Taper Reduced Neck Geometry Shot peened 127° & 132° CP Ti **Neck Angles** Plasma Spray **PureFix** HA Normalizations Stem length Polished Distal Tip

Figure 1: Secur-Fit Advanced A/P View

The only difference in the V40 taper of the Secur-Fit Advanced Hip Stem to the Accolade II is the taper length. The neck lengths of the Secur-Fit Advanced Hip Stem range from 26 mm to 40 mm and grow with stem size. Additionally, the necks are available in two angles (127° and 132°) that provide dual head offsets. Sizes 4 and 5 are available with a 132° offset angle only; all other

sizes are available in both 127° and 132° offset angles. Overall femoral offsets achievable with a +0 mm head range from 31.5 mm to 53.7 mm.

Table 1: Secur-Fit Advanced Stem Offsets

STEM	CATALOG NUMBER	NECK ANGLE	STEM SIZE	STEM LENGTH (mm)	NECK LENGTH (mm)	FEMORAL OFFSET WITH +0mm HEAD (mm)	DISTAL TIP DIAMETER* (mm)
	1601-06127	127	6	120	28	37.2	6.9
	1601-07127	127	7	130	32	41.5	7.4
Secur-Fit	1601-08127	127		136	32	42.4	8.1
Advanced 127°	1601-09127	127	9	142	36	46.9	8.9
ravanoca 127	1601-10127	127	10	148	36	48.1	9.7
	1601-11127	127	11	155	40	52.6	9.7
	1601-12127	127	12	160	40	53.7	10.7
	1601-04132	132	4	110	26	31.5	5.1
	1601-05132	132		115	26	32.5	6.0
	1601-06132	132	6	120	26	33.6	6.9
Coordin Ele	1601-07132	132		130	30	37.5	7.4
Secur-Fit Advanced 132°	1601-08132	132	8	136	30	38.4	8.1
Advanced 152	1601-09132	132	9	142	34	42.6	8.9
	1601-10132	132	10	148	34	43.8	9.7
	1601-11132	132	11	155	38	47.9	9.7
	1601-12132	132	12	160	38	49.0	10.7

The following femoral component catalog numbers are permissible according to this study protocol and are in the following format, where 'XX' varies by size:

1601-XX127 1601-XX132

The full listing of permissible femoral component catalog numbers may be found in Appendix D.

Additionally, only the following **Stryker compatible** ancillary devices may be used, according to this study protocol:

- Compatible Stryker femoral bearing heads
- o Compatible Stryker acetabular shells, liners and inserts

The compatible Stryker head and acetabular components are listed in the surgical protocol.

For reference, compatible femoral heads and acetabular components are listed in Table 2 and Table 3 below. In the case of any uncertainty regarding device compatibility, the current version of the Secur-Fit Advanced surgical protocol should be reviewed.

Table 2: Femoral Head Compatibility

HEAD	HEAD SIZE	HEAD OFFSETS
	22	+0, +3, +8
	26	-3, +0, +4, +8, +12
	28	-4, +0, +4, +8, +12
CoCr V40	32	-4, +0, +4, +8, +12
	36	-5, -4, +0, +4, +5, +8, +10
	40	-4, +0, +4, +8, +12
	44	-4, +0, +4, +8, +12
	28	-2.7, +0, +4
Alumina V40	32	-4, +0, +4
	36	-5, +0, +5
Alumina C-Taper	28	-2.5, +0, +5
(when used with C-Taper Sleeve –	32	-2.5, +0, +5
catalog # 17-0000E)	36	-5, +0, +5
	28	-4, -2.7, +0, +4
delta BIOLOX V40	32	-4, +0, +4
	36	-5, -2.5, +0, +2.5, +5, +7.5
delta BIOLOX C-Taper	28	-2.5, +0, +2.5, +5
(when used with C-Taper Sleeve –	32	-2.5, +0, +2.5, +5
catalog # 17-0000E)	36	-5, -2.5, +0, +2.5, +5, +7.5
	28	-2.5, +0, +4
delta BIOLOX Universal Taper (when	32	-2.5, +0, +4
used with Universal Taper Sleeve-	36	-2.5, +0, +4
catalog #6519-T-XXXX)	40	-2.5, +0, +4
	44	-2.5, +0, +4

^{*}Maximum head offset for Size 4 stem is +5

Table 3: Secur-Fit Advanced Compatible Acetabular Components

Trident X3 Acetabular Inserts
Trident Crossfire Elevated Rim Liners
Trident Crossfire Poly Liners, 10° or 0° profile
Trident Crossfire Eccentric Poly Liners, 10° or 0° profile
Trident Poly Liners, 10° or 0° profile
Trident Eccentric Poly Liners
Trident Constrained Insert
Crossfire Series II Inserts (2041C, 2042C, 2043C, S2301, S2302)
Series II Inserts, and Series II Eccentric Inserts
Constrained Liner
Series I Inserts
System 12 Inserts (Standard and Crossfire)
All Poly Cup
Trident All Poly Cup
Crossfire Trident All Poly Cup
UH1
Centrax Bipolar
PCA Acetabular Insert
Precision Acetabular Components
Trident N₂/Vac Polyethylene Inserts
Trident Hemispherical Solid Back Shells
Trident Hemispherical PS HA
Trident Hemispherical Shells (AD and AD-HA)
Trident PSL HA Solid Back Shells
Trident Hemispherical Cluster Shells
Trident PSL HA Cluster Shells
Trident Hemispherical Multi-Hole Shells
Tritanium Acetabular Shell System
Trident Porous Titanium Acetabular Components
Restoration ADM
MDM
Exeter X3 RimFit Cup

6.2 Device Retrieval Process

Stryker Orthopaedics will retrieve the Secur-Fit Advanced Hip Stem and/or adjacent tissues for analysis to help characterize potential device-related complications. In the event that the Secur-Fit Advanced Hip Stem is removed from a study subject, the procedure outlined in the Retrieved Implant Analysis Protocol (Appendix E) should be followed. In addition:

- 1. When revision of a study subject is scheduled, the study coordinator (SC) should contact the Clinical Study Manager (CSM) or other Stryker Clinical Research personnel assigned to the project, as soon as possible.
- 2. Stryker Clinical Research will send a retrieval container to the SC.
- 3. After the device is explanted, the SC or an identified Stryker field representative will retrieve the device and place it in the retrieval container, following the instructions in Appendix E.
- 4. The SC, an identified field representative or Stryker Clinical Research will complete a Product Experience Report (PER).
- 5. If not completed by Stryker Clinical Research, the PER should be faxed or emailed to Stryker Product Surveillance at [contact] or [contact], as well as to Stryker Clinical Research at [contact] or to the Clinical Research email addresses listed on the Sponsor Contact Sheet.
- 6. The PER should be attached to the retrieval container and sent to Product Surveillance.

 A de-identified operative report should be included, when available.
- 7. Stryker Clinical Research will follow up with Product Surveillance to obtain a PER number.
- 8. A summary of results will be provided to the investigator upon his/her request.

7 Evaluations

7.1 Preoperative Visit

During the preoperative visit, patients that are possible candidates for this study will be screened to determine if they meet the inclusion/exclusion criteria. If the patient is a candidate, the investigator will propose participation in the study to the patient, according to GCP guidelines. Patients must sign an IRB/EC approved Informed Patient Consent Form prior to participating in any study related activities. Consent must be obtained within 4 months prior to surgery.

Once the patient has been consented, preoperative data will be collected including: demographics, medical history, HHS, SF-12, LEAS, EQ-5D, AP pelvis and Lauenstein lateral radiographs. At sites participating in the preoperative planning subset, investigators will submit digital images of each subject's preoperative template as well as additional information regarding planned biomechanical parameters and devices to be implanted.

Version 3.0

All preoperative data must be collected within 4 months prior to the scheduled date of surgery,

Page 23

with the exception of radiographs, acceptable within 1 year prior to the scheduled date of surgery.

All information collected preoperatively will be used to quantify the sample population and

compare postoperative progress.

7.2 Surgery

Surgical details will be collected from the operative notes and at the time of surgery.

7.3 6-week Visit

During the 6-week visit (± 3 weeks), the following evaluations will be collected: HHS, SF-12,

LEAS, EQ-5D, AP pelvis and Lauenstein lateral radiographs.

In the event that an in-person visit cannot be conducted and radiographs cannot be obtained, a

Follow-up Questionnaire will be completed via mail, online completion (if available), or telephone

interview with the subject by investigative site personnel.

7.4 Annual Follow-up Visits

Clinical data will be collected via office visit by the investigator at the following annual

postoperative intervals: 1-year, 2-year and 5-year. Tools for postoperative evaluation at each of

these intervals will be the HHS, AP pelvis and Lauenstein lateral radiographs. In the event that

an in-person visit cannot be conducted and radiographs cannot be obtained, a Follow-up

Questionnaire will be completed via mail, online completion (if available), or telephone interview

with the subject by investigative site personnel.

Patient outcomes data will also be collected with the Follow-up Questionnaire, SF-12, LEAS, and

EQ-5D patient questionnaires at each office visit and at the 3-year and 4-year intervals via mail

or online completion, if available.

All clinical data, radiographs, and patient outcomes data must be collected within ± 2 months of

the 1-year and 2-year anniversary dates. For remaining annual time points, the window expands

to ± 3 months of the 3-year anniversary date and ± 4 months of the 4-year through

10-year anniversary dates.

The initial phase of the study will continue for 5 years after surgery and include collection of the previously described radiographs, HHS, SF-12, LEAS and EQ-5D patient questionnaires. In the second phase of the study, all subjects will complete a brief Follow-up Questionnaire annually at the 6-year, 7-year, 8-year, 9-year and 10-year follow-up intervals. This form may be completed by the SC during a subject telephone interview, or by the subject either at home or during a clinic visit. The questionnaire will be used to obtain the following information, at a minimum:

- Subject satisfaction with the hip replacement
- Presence of any pain in the study hip
- Any surgeries performed on the study hip

The questionnaire will also provide information on any revisions and enable calculation of the Kaplan-Meier Survival Curve.

Additionally, at investigational sites that choose to continue collecting clinical and radiographic data during the second phase of the study, subjects will be evaluated again at 7 and 10 years after surgery.

8 Adverse Events

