Preoperative Functional Evaluation	x												
Preoperative Digital Template	s												
Surgical Details		Х											
Postoperative Functional Evaluation			x	x	x			x		Optional			Optional
SF-12	X		X	Х	Х	Х	X	X		Optional			Optional
LEAS	Х		Х	Х	Х	Х	Х	Х		Optional			Optional
EQ-5D	Х		Х	Х	Х	Х	Х	Х		Optional			Optional
Lauenstein lateral and anteroposterior (AP) pelvis radiographs	x		x	x	x			x		Optional			Optional
Follow-up Questionnaire			As needed	As needed	As needed	x	х	As needed	x	x	х	х	х

X: Evaluation is required for all cases.

Functional Evaluation: The Functional Evaluations include the HHS, a subjective outcomes tool completed by the investigator that measures function, pain and motion.

SF-12: The SF-12 is a 12 item patient questionnaire that evaluates general health and well-being.

LEAS: The LEAS is a self-administered patient evaluation designed to reflect patient activity.

EQ-5D: The EQ-5D is a standardized instrument for use as a measure of health outcome.

Follow-up Questionnaire: The Follow-up Questionnaire is a short patient questionnaire intended to provide information on dislocation, patient satisfaction, pain and whether or not there have been any revisions or removals of the study device since the last follow-up visit.

S: Templating and preoperative plan will be collected for a subset of patients at select sites.

1 Introduction

This document is a protocol for a human research study. This study will be conducted in compliance with the protocol, Good Clinical Practice (GCP) Standards, associated Federal regulations and all applicable research requirements.

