2.1.3 Additional Data Collection

Clinical Outcomes:

Clinical outcomes will be evaluated with the total HHS, including pain, motion and function, preoperatively and at the 6-week, 1, 2 and 5-year visits. Additional HHS data will be obtained at the 7-year and 10-year time points at investigational sites that choose to bring their subjects in for these optional visits.

Patient Outcomes:

Pain, function and health related QOL will be compared between the Secur-Fit Advanced Hip Stem and reports in the literature for other primary femoral stems on the market. The SF-12 is a 12 item patient self-assessment evaluating health and general well-being. The LEAS is a tool that has been developed and validated to evaluate the level of patient activity. The EQ-5D is a standardized instrument for use as a measure of health outcome. These tools will be used to assess patient health-related QOL and will be collected preoperatively and at the 6-week, 1, 2, 3, 4, and 5-year time points.

A Follow-up Questionnaire will be administered annually in postoperative years 3, 4 and 6-10 to assess patient satisfaction and pain, and to capture AEs. This questionnaire, which will also be completed during each interval through 5 years postoperative at which the subject is not seen by the investigator, will provide the information necessary to create an accurate Kaplan-Meier Survival Curve. Patient outcomes data will also be obtained at the 7-year and 10-year time points at investigational sites that choose to bring their subjects back in for these optional visits, in addition to the required Follow-up Questionnaire described.

Radiographic Outcomes:

To assess radiographic stability as compared with other primary femoral stems, radiographs will be taken and collected in the low AP pelvis and Lauenstein lateral views for the preoperative, 6-week, 1, 2 and 5-year intervals. Additional radiographs will be obtained at the 7-year and 10-year time points at investigational sites that choose to bring their subjects back in for these optional visits.

The low AP pelvis view allows for measurement of the position of the hip center, femoral offset and neck angle, and any leg length discrepancy. The Lauenstein lateral view allows for evaluation of the entire hip joint as well as the femoral head, neck and proximal shaft. Suggested radiographic technique for the views required is included in Appendix C.

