9.4 Statistical Methodology

9.4.1 Data Summary

Descriptive statistics will be computed for all baseline conditions and demographic parameters. That is, for continuous data, the N, mean, median, standard deviation, minimum and maximum will be computed. For categorical data, the frequency will be computed. The data will be presented by appropriate subgroups (e.g., center, gender).

A Kaplan-Meier survivorship curve will be displayed for revision and/or removal of the Secur-Fit Advanced Hip Stem for aseptic loosening or device-related femoral fracture.

A Kaplan-Meier survivorship curve will be displayed for all-cause revision and/or removal of the Secur-Fit Advanced Hip Stem.

For the additional data collected according to Section 2.1.3, data will be summarized according to visit. For parameters represented by continuous variables (e.g., ROM), the

summaries will consist of the N, mean, median, standard deviation, minimum, and maximum values. For categorical variables (e.g., Mobility from EQ-5D), the frequency and percentage in each category will be presented. A paired t-test will be performed to evaluate the change in clinical and patient outcomes, preoperative to 5 years within the Secur-Fit Advanced Hip Stem. The 1-year, 2-year and 5-year SF-12, LEAS and HHS will be presented with respect to improvement from preoperative scores.

For the Follow-up Questionnaire, frequency and percentage will be computed for each category according to visits. Applicable lists based on Follow-up Questionnaire will be generated to capture AEs.

For radiographic data, data will be presented according to visits for available parameters. Frequency and percentage will be computed for radiolucency according to visit. Lists will be generated for migration over time. Radiographic failure will be evaluated, where radiographic failure is defined as subsidence of greater than 5 mm, migration of greater than 5° in any direction or at least 2 mm radiolucency in all zones within a single view.

Documentation of statistical analyses utilizing SAS® software version 9.1.3 or higher.

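### No remote route is given for SF-12, LEAS and EQ-5D when a 6-week, 1-, 2- or 5-year visit is missed, although the schedule requires them of every case and years 3 and 4 already use mail or online completion

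*Combined protocol and SAP*

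**What the plan says.** **Fallback for a missed visit.** Section 7.4 sets office visits at years 1, 2 and 5, with HHS and radiographs. If "an in-person visit cannot be conducted and radiographs cannot be obtained, a Follow-up" form takes their place: "Questionnaire will be completed via mail, online completion (if available), or telephone interview" with site staff. Section 7.3 has the same rule at 6 weeks, triggered when "an in-person visit cannot be conducted and radiographs cannot be obtained, a" Follow-up Questionnaire being again the only form named. Section 2.1.3 repeats it, describing the questionnaire as one "which will also be completed during each interval through 5 years postoperative at which the subject is not seen by the investigator".

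**Route for the three scales.** The next paragraph of 7.4 collects the SF-12, LEAS and "EQ-5D patient questionnaires at each office visit and at the 3-year and 4-year intervals via mail" or online.

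**What is required.** Section 2.1.3 says the scales "will be collected preoperatively and at the 6-week, 1, 2, 3, 4, and 5-year time points". The Evaluation Schedule puts an X against each of them at 6 weeks and at years 1 to 5, with the key "X: Evaluation is required for all cases". The schedule lists the Follow-up Questionnaire for use as needed at 6 weeks and years 1, 2 and 5, and describes its content as dislocation, satisfaction, pain and revisions or removals.

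**What is analysed.** Section 9.4.1 summarises the additional data by visit, presents SF-12, LEAS and HHS at 1, 2 and 5 years as improvement from preoperative, and adds a test: "A paired t-test will be performed to evaluate the change in clinical and patient outcomes, preoperative to 5 years". Section 9.3 imputes nothing.

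**The concern.** The HHS and the radiographs need the subject in the clinic. The three scales do not: the protocol describes the SF-12 as a self-assessment and the LEAS as self-administered, and 7.4 groups all three as patient questionnaires with a mail or online route at years 3 and 4. A subject who misses the visit but completes the Follow-up Questionnaire has, by definition, been reached. The fallback nevertheless names a form that cannot stand in for the scales, and gives sites no instruction for obtaining them.

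At stake are the function and quality-of-life results at 1, 2 and 5 years, which the synopsis and section 2.1.3 intend to set against published results for other stems. If the text is applied as written, those results come from attendees only. Missed visits are foreseen: the plan writes a fallback for them, and section 15.3 describes subjects losing insurance and carriers refusing visits or referrals. Attendance may therefore not be random.

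**Working it through.** **1. Reading the text.**

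| Time point | Scales required (schedule, 2.1.3) | Route stated for scales | Form named if visit is missed |
|---|---|---|---|
| 6 weeks | yes | visit (7.3) | Follow-up Questionnaire |
| Years 1, 2, 5 | yes | office visit (7.4) | Follow-up Questionnaire |
| Years 3, 4 | yes | mail or online (7.4) | not applicable, no office visit |

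The gap lies in the first two rows: data are required, and no route is stated once the visit fails.

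**2. Which analyses are touched.** By-visit summaries of all three scales; the improvement presentation for SF-12 and LEAS at years 1, 2 and 5 (EQ-5D is not part of it, nor is 6 weeks); and the paired t-test from preoperative to 5 years. With no imputation, a missing 5-year score removes the pair.

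**3. Planned loss to follow-up.** Section 9.4.2 inflates 277 evaluable cases for 15% loss: 277 / (1 − 0.15) = 325.9, which rounds up to the stated 326. The same rate on the current target of 314 (section 3.3) leaves 314 × 0.85 = 266.9, about 267 cases.

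**4. Size of the gap at 5 years.** The documents give no rate of missed visits among subjects still reachable. Let m be the share of the 267 who miss the 5-year visit but answer the questionnaire; 5% to 15% is an assumed range.

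| m | Scores missing (266.9 × m) | Cases left |
|---|---|---|
| 5% | 13 | 267 − 13 = 254 |
| 10% | 27 | 267 − 27 = 240 |
| 15% | 40 | 267 − 40 = 227 |

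These are upper figures for what the fix could recover, since not every questionnaire responder would return three more forms.

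**5. Effect on the mean change.** Let A be the mean change in attendees, N that in reachable non-attendees, and D = A − N. The mean over all reachable cases is (1 − m)A + mN. Reporting A instead is off by A − [(1 − m)A + mN] = mD, that is 0.05D to 0.15D over the assumed range. The documents give neither the size nor the sign of D, and no scale range or standard deviation for the three instruments, so no figure in points can be given.

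**6. Effect on precision.** With the same standard deviation, the standard error grows by 1/√(1 − m): 1/√0.95 = 1.026 and 1/√0.85 = 1.085, or about 3% to 8%. Selection is the larger worry.

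**The case against.** The best counter-argument is that the scales are still required. The schedule's X carries no condition on attendance, 2.1.3 says the scales will be collected at those times, and nothing forbids mailing them. In 7.4 the fallback closes the paragraph on HHS and radiographs, while the patient forms come in a separate paragraph. On that reading the fallback replaces the clinical assessment and waives nothing. This stands in part. A reader might infer that the plan discards these scores; the documents do not support that, only that no remote route is stated. The reading is also weaker at 6 weeks, because 7.3 lists the scales among the visit's evaluations and follows them directly with the fallback. Even in 7.4, the scales are tied to an office visit that has not taken place.

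Two other stronger readings are tempting:

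- *That the published comparison will flatter the stem because the sicker subjects stay away.* Nothing in the documents says non-attendees do worse. Their pain and satisfaction are still recorded on the questionnaire, and the scales are sent remotely at years 3 and 4, so they are not unobserved. The direction of any bias is unknown.
- *That the main result is weakened.* The questionnaire captures revisions and removals, so the primary endpoint is untouched. The scales fall under additional data collection and are neither primary nor secondary parameters (9.1.1, 9.1.2).

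Timing also counts. Section 9.4.2 refers to enrolment falling after 2018, so some early visits have probably passed and a change helps only later ones.

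**Conclusion.** The point holds as a gap between what the schedule requires and what sections 7.3, 7.4 and 2.1.3 tell sites to do after a missed visit. Applied as written, the fallback yields less data than a contact already being made could yield, at time points the analysis uses. On the assumption that 5% to 15% of about 267 reachable cases miss the 5-year visit but answer the questionnaire, about 13 to 40 paired scores would be missing, and the mean change would be off by 0.05 to 0.15 times an unknown difference of unknown sign. Both ends rest on an assumed rate and on the planned 15% loss being realised. If sites already mail the scales when a visit is missed, the practical loss is smaller and the text only needs to say so. The consequence is confined to additional-data outcomes, but the remedy is cheap enough that it should be made.

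**What to change.** In 7.3 and 7.4, state that when an in-person visit cannot be conducted, the SF-12, LEAS and EQ-5D will be completed by mail or online (if available), in addition to the Follow-up Questionnaire. This is the route 7.4 already uses at years 3 and 4. Apply it to all visits still to come. Record the mode of completion for each form, and align section 2.1.3 and the notes to the Evaluation Schedule. Only the HHS and radiographs would then be missing by design after a missed visit.

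Do not add telephone administration of these three scales. The telephone option in the fallback belongs to the Follow-up Questionnaire; years 3 and 4 use mail or online only, and staff-administered completion would be a new mode for forms described as self-completed.

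Cost: a short amendment with EC/IRB submission (section 14), three brief forms sent to subjects already being contacted (a separate mailing or link where the questionnaire is done by telephone), and mixed modes of completion at the affected visits, which the recorded mode allows the analyst to examine.
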